2.4.3.2 Medical history date of diagnosis imputation

Completely missing dates will not be imputed. Partial dates of diagnosis will be compared to the treatment start date.

- If DIAG year < treatment start date year and DIAG month is missing, the imputed DIAG date is set to the mid-year point (01JULYYYY)
 - else if DIAG month is not missing, the imputed DIAG date is set to the mid-month point (15MONYYYY)
- If DIAG year = treatment start date year
 - and (DIAG month is missing OR DIAG month is equal to treatment start month), the imputed DIAG date is set to one day before treatment start date
 - else if DIAG month < treatment start month, the imputed DIAG date is set to the midmonth point (15MON YYYY)
 - else if DIAG month > treatment start month => data error
- If DIAG year > treatment start date year => data error

2.4.3.3 Concomitant treatment date imputation

In order to classify a medication as prior or prior/concomitant, it may be necessary to impute the start date. Concomitant treatments with partial start dates will have the date or dates imputed. Partial concomitant treatment start dates are imputed with reference to the treatment start date (TRTSTD) in accordance with the rules outlined below:

Concomitant treatments with completely missing start dates will not be imputed. As a conservative approach, such treatments will be classified as prior/concomitant (i.e. as being received on or after the start of study treatment).

	Day	Month	Year
Partial CMD Start Date	Not used	MON	YYYY
Treatment Start Date (TRTSTD)	Not used	TRTM	TRTY

The following matrix explains the logic behind the imputation.

Comparison of Month Section	MON MISSING	MON<TRTM	MON=TRTM	MON>TRTM
YYYY MISSING	(C) Uncertain	(C) Uncertain	(C) Uncertain	(C) Uncertain
YYYY<TRTY	(D)=01JULYYYY Before Treatment Start	(A)=15MONYYYY Before Treatment Start	(A)=15MONYYYY Before Treatment Start	(A)=15MONYYYY Before Treatment Start
YYYY=TRTY	(C) Uncertain	(A)=15MONYYYY Before Treatment Start	(C) Uncertain	(B)=01MONYYYY After Treatment Start
YYYY=TRTY	(E)=01JANYYYY After Treatment Start	(B)=01MONYYYY After Treatment Start	(B)=01MONYYYY After Treatment Start	(B)=01MONYYYY After Treatment Start

The following table is the legend to the logic matrix.

Relationship	
Before Treatment Start	Partial date indicates CMD start date prior to Treatment Start Date
After Treatment Start	Partial date indicates CMD start date after Treatment Start Date
Uncertain	Partial date insufficient to determine relationship of CMD start date to Treatment Start Date
Imputation Calculation	
NC / Blank Uncertain	No convention
(A) Before Treatment Start	15MONYYYY
(B) After Treatment Start	MAX(01MONYYYY,TRTSTD+1)
(C) Uncertain	IF CMDTYP1C IN (1, 3) THEN TRTSTD-1 ELSE IF CMDTYP1C IN (. 2) THEN TRTSTD+1
(D) Before Treatment Start	01JULYYYY
(E) After Treatment Start	01JANYYYY

2.5 Subject disposition, background and demographic characteristics

2.5.1 Subject disposition

The number of subjects randomized and included in each of the analysis sets will be presented by treatment group. The number and percentage of subjects in the Full Analysis Set (FAS) who completed the study, who discontinued the study and the reason for discontinuation will be presented for each treatment group and all subjects.

The number of subjects screened only will also be presented. In addition, the reasons for screen failures will be provided.

An additional table will summarise and compare the number of subjects randomized by treatment group and site.

2.5.2 Protocol deviations

All clinically significant protocol deviations will be summarized by number and percentage of patients with each deviation. Patients with multiple protocol deviations will only be counted once at each level of summarization. In addition, a listing of protocol deviations will be produced including the date and study day of the deviation occurrence with the accompanying deviation code and severity. Deviations will be summarized for the Randomized Set. Refer to the protocol deviation plan for the PDs / non-PDs defined for this study.

Note that protocol deviations may lead to exclusion of data based on a per-patient, per-visit or per-variable basis, as described in the protocol deviation plan.

2.5.3 Background and demographic characteristics

The following background and demographic variables will be analysed using the Randomised Set:

Continuous variables (per eCRF):

- Age (years)

Categorical variables (per eCRF):

- Gender (Male, Female)
- Race, grouped as
 - Caucasian: Afghan, Caucasian, Egypt, Egyptian, El Salvadore, Greek, Hispanic, Israeli, Italian, Maltese, Middle East, Middle Eastern, South American, Turkish, Yugoslavian
 - Black African
 - Asian: Asian and Indian;
 - Aboriginal and Torres Strait Islander
 - Pacific Islander
 - Not sure
- Ethnicity (Anglo Saxon, Northern European, Southern European, Asian Indian, Other)

For continuous variables, descriptive statistics (mean, median, standard deviation, minimum and maximum) will be presented for each treatment group and for all subjects (total).

For categorical variables, the number and percentage of subjects in each category will be presented for categorical variables for each treatment group and all subjects (total). The number and percentage of subjects with missing data will also be presented.

2.5.4 Eligibility

All eligibility data, including inclusion and exclusion criteria, will be listed.

2.5.5 Baseline Characteristics

The following baseline characteristic variables will be analysed using the Randomised Set:

Categorical baseline variables (per eCRF):

- Study eye selection (L/R)
- Prior wet AMD treatment for fellow eye (Yes/No)
- Prior wet AMD treatment for fellow eye (Lucentis, Eylea, Visudyne, Avastin, Steroids, Other)
- Family history of AMD
- History of thromboembolic events
- Smoking history (as reported, as well as grouped with “Never smoked” and “Smoked in the past” combined)

Continuous baseline efficacy variables:

- Total BCVA score (per eCRF)
- OCT assessments (per [REDACTED]):
 - Central subfield foveal thickness (CSFT) (μm^2)
 - Central subfield volume (mm^3)
- FA assessments (per [REDACTED]):
 - Area of lesion (mm^2)
 - Area of CNV (mm^2)
 - Area of Geographic atrophy (mm^2)

Categorical baseline efficacy variables

- Visual acuity ≥ 70 letters (20/40) - per eCRF
- Visual acuity < 70 letters – per eCRF
- OCT assessments (per [REDACTED]):
 - Intra-retinal fluid (Present, Absent, Can't grade) (within 6x6mm scan) (also per eCRF)
 - Intra-retinal fluid centre involvement (Present, Absent, Can't grade)
 - Intra-retinal cysts (Present, Absent)
 - Intra-retinal cysts centre involvement (Present, Absent)
 - Sub-retinal fluid (Present, Absent, Can't grade) (within 6x6mm scan) (also per eCRF)
 - Sub-retinal fluid centre involvement (Present, Absent, Can't grade) (within 6x6mm scan)
 - Sub-retinal fluid at centrepoint (Present, Absent, Can't grade)
 - Sub-retinal fluid height at centrepoint ($> 200\mu\text{m}$, $\leq 200\mu\text{m}$, not applicable) (also per eCRF)
 - Morphologic changes (epiretinal membrane, vitreoretinal traction, macular hole, atrophy, other)
- FA assessments (per [REDACTED]):
 - CNV complex (lesion) (Absent, Definite, Questionable etc.) (also per eCRF)
 - CNV complex (lesion) location (subfoveal, juxtafoveal, extrafoveal, can't grade)
 - CNV complex (lesion) location (subfoveal, juxtafoveal, extrafoveal, can't grade), by presence of fluid central involvement
 - CNV location (subfoveal, juxtafoveal, extrafoveal, can't grade) (also per eCRF)
 - CNV location (subfoveal, juxtafoveal, extrafoveal, can't grade), by presence of fluid central involvement
 - CNV secondary to (AMD, angioid streaks, idiopathic, pathologic myopia, other)
 - Type of CNV (predominantly class, occult, fibrovascular PED, serous PED, other)
 - CNV leakage (Present, Absent)
 - Lesion components (CNV, blood, serous PED, RPE tear, can't grade, other)
 - Geographic atrophy (Absent, Definite, Can't grade etc.)
 - Geographic atrophy location (central subfield, inner subfield, outer subfield)

- Colour fundus assessments (per [REDACTED]):
 - Haemorrhage (Absent, definite, Can't grade, NA)
 - Haemorrhage location (central subfield, inner subfield, outer subfield)
 - Retinal abnormality (drusen, atrophy, fibrosis, PED, other) (Present, Absent)
 - Retinal abnormality location (central, periphery)

Summary statistics will be presented for each treatment group and for all subjects (total) in the Randomised Set, for all baseline characteristics (including the baseline values of the main efficacy endpoints).

For continuous variables, descriptive statistics will be presented.

For categorical variables, the number and percentage of subjects in each category will be presented for categorical variables for each treatment group and all subjects (total). The number and percentage of subjects with missing data will also be presented.

An analysis will be conducted to compare baseline age, visual acuity, lesion size, SRF and IRF between those participants who provided a saliva sample and those who did not.

Study Endpoint	Method of Analysis
Comparison of baseline visual acuity between participants who provided a genotyping saliva sample and those who did not	Mixed Model
Comparison of baseline SRF between participants who provided a genotyping saliva sample and those who did not	Logistic regression model
Comparison of baseline IRF between participants who provided a genotyping saliva sample and those who did not	Logistic regression model
Comparison of age between participants who provided a genotyping saliva sample and those who did not	Mixed Model
Comparison of lesion size between participants who provided a genotyping saliva sample and those who did not	Mixed Model

The mixed model analyses will include genotype saliva sample status as a definite class variable and treatment group as an optional class variable. Further details regarding the general mixed model approach are detailed in Section 2.8.2.5.

Logistic Regression analyses will include genotype saliva sample status as the predictor variable. Further details regarding the general logistic regression approach are detailed in Section 2.8.2.5.

2.5.6 Medical history

Relevant medical history (ocular and non-ocular) and current medical conditions will be tabulated by system organ class and preferred term of the MedDRA dictionary. Separate tables will be provided for ocular (study eye and fellow eye) and non-ocular histories and conditions. The number and percentage of subjects with each medical condition will be provided by treatment group for the Randomised Set.

Additionally, all information will be listed including the investigator reported term, and the diagnosis/surgery date and day.

2.6 Study medication

The following summaries will be presented for the injections in the study eye and the fellow treated eye using the Safety Set:

- Duration of Exposure
 - Descriptive statistics (mean, median, standard deviation, minimum and maximum) will be presented using days as the unit.
- The number of ranibizumab injections presented by treatment group in frequency tables by visit and cumulatively.

Analyses of the treatment exposure and treatment patterns of the two alternative treatment regimens over 24 months include:

- Treatment frequency
- Total number of injections
- Reason for interval decision (as defined within disease activity for each arm)

The number of injections administered per patient for injections in the study eye will be summarized. Both the frequency distribution (number of patients with 1 injection, number of patients with 2 injections, on up to the maximum number of injections for any one patient for the given treatment period) and summary statistics for the number of injections per patient will be presented.

Additionally, a listing of summarized dosing parameters (e.g., total number of injections in the study eye) will be provided. A listing will also be provided detailing data related to the study observation period.

Furthermore, to assess visit/treatment frequency and average visit/dosing interval, the following summaries will be provided (within the FAS)

- The number (%) of patients by the maximum visit interval (4, 6, 8, 10 and 12 weeks); a visit interval is defined as the difference of the visit week number as from the visit date. E.g. if the first visit to be considered is recorded as Week 16 visit and the next visit is recorded as Week 22 visit, then the visit interval is 6 weeks; the maximum visit interval is evaluated on a patient level, i.e. the longest visit interval within the study for each patient.

- The number (%) of patients for whom the visit interval was never decreased, decreased once, decreased two times; The decrease of the visit interval is based on a comparison with the previous visit interval. E.g. if the previous visit interval was 8 weeks and the current visit interval is 6 weeks (4 weeks), then the visit interval was decreased by 2 weeks (4 weeks).
- The number (%) of patients by breakpoint interval (4, 6, 8, 10 and 12 weeks); (the injection interval equals the visit interval)
- The number (%) of patients by the number of times the patient returned to monthly injections.
- The number (%) of patients with presence of new haemorrhage, fluid (SRF, IRF) or a loss of visual acuity of ≥ 5 letters related to study indication, by visit and disease activity (over all post-baseline visits).
- The number (%) of patients with presence of vision impairment attributable to disease activity related to study indication, by visit (over all post-baseline visits).
- The number of scheduled and attended post-baseline visits by patients will be summarized (i.e. all scheduled and attended visits after baseline).
- The number of injections by patients will be summarized. Injections administered on, or after, the Month 12 visit, will count towards the 2nd year of treatment.
- The average time (in days) between visits scheduled for treatment will be summarized; the time “delta” between 2 consecutive visits will be calculated as: $\text{delta} = (\text{Date of visit } x) - (\text{date of visit } x-1) + 1$; the average per patients will then be summarized.

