## Section 12 Safety evaluation

### EXTENT OF EXPOSURE

**Table 12.1-1 Overall exposure**  
Safety Set

|                              | Intensive
(N=X) | Relaxed
(N=X) | Total
(N=X) |
|------------------------------|--------------------|------------------|----------------|
| Duration of Exposure (days)* |                    |                  |                |
| n                            | x                  | x                | x              |
| Mean                         | x.x                | x.x              | x.x            |
| Median                       | x.x                | x.x              | x.x            |
| SD                           | x.x                | x.x              | x.x            |
| Minimum                      | x                  | x                | x              |
| Maximum                      | x                  | x                | x              |

SD: Standard Deviation

\*Duration of Exposure = Date of first treatment to date of End of Treatment + 1

Source: Table 14.3-2

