**Table 14.2-11 Treatment Interval Summary (Based on Actual Intervals between Visits)**

Full Analysis Set and Per-Protocol Set

| Statistic | Intensive
(N=X) | Relaxed
(N=X) | Total
(N=X) |
|-----------|--------------------|------------------|----------------|
| n         | x                  | x                | x              |
| Mean      | x.x                | x.x              | x.x            |
| Median    | x.x                | x.x              | x.x            |
| SD        | x.x                | x.x              | x.x            |
| Minimum   | x                  | x                | x              |
| Maximum   | x                  | x                | x              |

SD: Standard Deviation

Average treatment interval for each group - need to average it out for patient then average out for the treatment arm

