**Table 14.3-2 Duration of exposure to study drug, by treatment**

Safety Set

|                              | Intensive
(N=X) | Relaxed
(N=X) | Total
(N=X) |
|------------------------------|--------------------|------------------|----------------|
| Duration of Exposure (days)* |                    |                  |                |
| n                            | x                  | x                | x              |
| Mean                         | x.x                | x.x              | x.x            |
| Median                       | x.x                | x.x              | x.x            |
| SD                           | x.x                | x.x              | x.x            |
| Minimum                      | x                  | x                | x              |
| Maximum                      | x                  | x                | x              |

SD: Standard Deviation

\*Duration of Exposure = Date of first treatment to date of End of Treatment

**Table 14.3-3 Medications and significant non-drug therapies taken prior to the start of study drug by ATC class, preferred term and treatment**

Safety Set

| Anatomic Therapeutic Classification (ATC)
Preferred Term (PT) | Intensive
(N=X) | Relaxed
(N=X) | Total
(N=X) |
|--|--------------------|------------------|----------------|
| Any ATC Class with medication/surgery                            | x (xx.x)           | x (xx.x)         | x (xx.x)       |
| Nr of concomitant medications reported                           | x                  | x                | x              |
| ATC1   | x (xx.x)           | x (xx.x)         | x (xx.x)       |
| PT1  | x (xx.x)           | x (xx.x)         | x (xx.x)       |
| PT2  | x (xx.x)           | x (xx.x)         | x (xx.x)       |
| ....   | ....               | ....             | ....           |
| PTx  | x (xx.x)           | x (xx.x)         | x (xx.x)       |
| ATC1   | x (xx.x)           | x (xx.x)         | x (xx.x)       |
| PT1  | x (xx.x)           | x (xx.x)         | x (xx.x)       |
| PT2  | x (xx.x)           | x (xx.x)         | x (xx.x)       |
| ....   | ....               | ....             | ....           |
| PTx  | x (xx.x)           | x (xx.x)         | x (xx.x)       |

.....  
Note: Patients who take the same medication (in terms of the preferred term) more than once will be counted only once for that medication.

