2.4.1.2 Post-baseline

All assessments obtained after the date of first dose of study drug are considered as post-baseline unless otherwise specified. Missing data for post-baseline values, for example due to discontinuation, loss to follow-up, or other types of censoring (e.g. due to rescue medication), will not be imputed. Only subjects with measurements at any given time point will be included in the analysis for that given parameter and visit. Refer to Section 2.4.3 for further details regarding the handling of missing dates.

The study day for a baseline or post-baseline scheduled or unscheduled visit is defined as:

$$\text{Study day} = (\text{Date of visit}) - (\text{date of first treatment}) + 1$$

The study day for a scheduled or unscheduled visit before baseline is defined as:

$$\text{Study day} = (\text{Date of visit}) - (\text{date of first treatment})$$

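### The SAP's formula for days between consecutive treatment visits adds one day to every gap, so a 28-day interval is reported as 29

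*SAP*

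**What the plan says.** SAP section 2.6 (Study medication) lists several summaries of visit and dosing intervals for the Full Analysis Set. The last reads "The average time (in days) between visits scheduled for treatment will be summarized". It defines delta for two consecutive visits as the date of visit x, minus the date of visit x-1, plus 1. The deltas are averaged within each patient and the patient averages are then summarised.

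Two other SAP rules bear on this:

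- Earlier in section 2.6, "a visit interval is defined as the difference of the visit week number as from the visit date". The example given there is that Week 16 followed by Week 22 is an interval of 6 weeks. Nothing is added.
- Section 2.4.1.2 defines the study day of a baseline or later visit as its date minus the date of first treatment, plus 1, so the first treatment day is Day 1.

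Among the output shells in the Protocol document, Table 14.2-11 summarises actual intervals between visits, averaged by patient and then by arm. It gives no formula and no unit.

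**The concern.** A plus 1 belongs in a rule that numbers days from a Day 1, or that counts the days of one span including both ends. It does not belong in a measure of time between two visits. Applied to a chain of consecutive visits, it counts each shared visit day twice.

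The retreatment interval is what the two regimens are meant to vary, so this summary is a planned description of how they were delivered. The shells pair an interval summary based on the investigator's interval decision (Table 14.2-10) with one based on actual intervals (Table 14.2-11). If the second used delta, patients seen exactly on time would appear one day late at every visit.

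**Working it through.** **Inputs**

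- Gap formula: delta = date(x) − date(x−1) + 1 (SAP 2.6).
- Study day: date − date of first treatment + 1 (SAP 2.4.1.2).
- Visit interval: plain difference of week numbers, Week 16 to Week 22 = 6 weeks (SAP 2.6).
- Possible intervals: 4, 6, 8, 10 and 12 weeks (SAP 2.6).

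The SAP prints no numerical value of delta. The 28 and 29 days used here follow from the 4-week interval and the formula.

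**Step 1. The SAP's own example.** With visits exactly on schedule, Week 16 to Week 22 is 6 × 7 = 42 days by plain difference, which reproduces the stated 6 weeks. Delta for the same two dates is 42 + 1 = 43 days, or 43/7 = 6.14 weeks.

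**Step 2. The study-day rule.** Let d0 be the date of first treatment. The difference between the study days of two visits is

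(d_x − d0 + 1) − (d_{x−1} − d0 + 1) = d_x − d_{x−1}.

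The plus 1 cancels. Day 57 minus Day 29 is 28 days, whereas delta gives 29. This step needs no assumption about visit windows.

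**Step 3. Size for each interval.**

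| Interval | Elapsed days | Delta | Excess |
|---|---|---|---|
| 4 weeks | 28 | 29 | 1/28 = 3.6% |
| 6 weeks | 42 | 43 | 1/42 = 2.4% |
| 8 weeks | 56 | 57 | 1/56 = 1.8% |
| 10 weeks | 70 | 71 | 1/70 = 1.4% |
| 12 weeks | 84 | 85 | 1/84 = 1.2% |

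**Step 4. Averaging does not remove it.** For a patient with k gaps, the deltas sum to (last date − first date) + k. Their mean is therefore (last date − first date)/k + 1, one day above the true mean whatever the value of k.

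To show the double counting, take 104 weeks (728 days) with on-time visits. This is an assumption, because the visit schedule in protocol section 5.5.4.1 is not in the documents.

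- 26 four-week gaps: 26 × 29 = 754 days, mean 754/26 = 29.0 against 728/26 = 28.0.
- Two 4-week and eight 12-week gaps: 2 × 29 + 8 × 85 = 738 days, against 2 × 28 + 8 × 84 = 728.

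**Step 5. What is left unchanged.** Adding a constant to every patient's average does not alter the SD. It also cancels between arms: if one arm averaged 10 weeks and the other 8, the difference would be 71 − 57 = 14 days, the same as 70 − 56 = 14.

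**Secondary check: exposure.** The footnote to Table 12.1-1 defines duration of exposure as "Date of first treatment to date of End of Treatment + 1". Its cited source, Table 14.3-2, has "Duration of Exposure = Date of first treatment to date of End of Treatment", with nothing added. Read literally, the text table and its source differ by one day.

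**The case against.** The strongest defence is that the plus 1 is a stated convention. SAP section 2.4.2 defines the study observation period as the days between first treatment and the end-of-study visit, plus 1, so the SAP does count inclusively elsewhere, and delta could be read the same way. That suits a single span with one first and one last day. It does not suit the time between consecutive visits, where the last day of one gap is the first day of the next.

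Other points stand in part:

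- The visit interval in section 2.6 is a difference of derived week labels, and section 2.4.1.3 gives those labels windows of ±7 days. The contrast of 42 with 43 days therefore holds only for visits on the exact days, and the two summaries can differ for that reason too. The study-day argument does not depend on this and is enough alone.
- No shell is shown to use delta.
- The SAP never sums the deltas, so 754 and 738 days are illustrations and not reportable totals. The ten-gap schedule has visits at Weeks 44 and 56. If an on-time Month 12 visit at Week 52 also had to count, at least 2 + 4 + 5 = 11 gaps would be needed. The excess of one day per gap stays the same.
- The exposure footnotes concern a different variable and neither support nor depend on the delta point.
- The practical effect is small, and no decision in the trial rests on it.

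**Conclusion.** The formula is wrong as written for time between visits. Each gap, each patient's average, and each arm's mean, median, minimum and maximum of this summary are exactly one day too high. This follows from the SAP's text and needs no assumption; only the 104-week illustrations assume on-time visits.

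Whether Table 14.2-11 carries the error is unknown, because its shell does not say how the interval is calculated. The week-based and interval-decision summaries, the injection-count model and the BCVA analyses are unaffected. The correction is desirable rather than essential.

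**What to change.** Delete the plus 1 from delta in SAP section 2.6, so that it is the plain difference between consecutive visit dates in days. State that formula and its unit in a footnote to Table 14.2-11.

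As a separate tidy-up, use one exposure formula in the footnotes of Tables 12.1-1 and 14.3-2. The inclusive form, with the plus 1, is appropriate there because exposure is a single span, and it matches the observation-period rule in SAP section 2.4.2.

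The cost is one term in one formula and short footnotes in three shells. No data collection, sample size or inferential analysis changes.
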